**Causal Lesion Network Guided Treatment of Bipolar Mania
With Transcranial Electrical Stimulation**

NCT #: NCT05445466

June 23, 2025

Protocol Number:	2022P000295
Title:	Causal Lesion Network Guided Treatment of Bipolar Mania With Transcranial Electrical Stimulation
Design:	Double blind, design with baseline, day 5, 1 month and 3 month follow up visits during which transcranial electrical stimulation (tES) was delivered to the right orbital frontal cortex (rOFC) from baseline to day 5 each day (5 days) twice a day for 20 mins. Participants were randomly assigned to either cathodal transcranial direct current (tDCS), 10hz or personalized transcranial alternating current (tACS) conditions to test the effectiveness and feasibility of stimulating the rOFC using a novel targeting methodology consisting of a lesion network guided brain target linked to mania symptoms.
Objectives:	Evaluate the effectiveness and safety of transcranial electrical stimulation for improving the mania symptoms
Enrollment:	14 Individuals
Clinical Sites:	Beth Israel Deaconess Medical Center, Boston, MA
Patient Population:	Male or female outpatients 18-65 years of age patient's diagnosis with either bipolar or schizoaffective disorder, or history of mania as defined by DSM-5 or DSM-IV-TR criteria
Primary and Secondary Outcomes:	Primary Outcomes: Young Mania Rating Scale (YMRS); Altman Self-Rated Mania Scale (ASRM); Average Hospitalizations Secondary Outcomes: Balloon Analogue Risk Task (BART); The Go/No Go Task; Reinforcement Learning Task (RLT); Social Functioning Scale (SFS); Positive and Negative Syndrome Scale (PANSS); Global Assessment of Functioning (GAF); Barret Impulsiveness Scale (BIS); Resting State EEG; Brief Assessment of Cognition (BAC); Montgomery-Asberg Depression Rating Scale (MADRS)
Inclusion Criteria:	
 1. Aged 18-65 years of age 2. Proficient in English 3. Able to give informed consent 4. Meet diagnostic criteria for bipolar disorder or schizoaffective disorder, bipolar type as verified by the SCID 5. History of mania (>1 lifetime episode) 6. Experiencing mild to moderate symptoms of mania 7. No changes to mood stabilizing medications for a period of 2 weeks prior to participation 8. Has not recently participated in tES/TMS treatments

	In addition to the criteria above, participants for this stimulation procedure will be included if they have a history of mania and may or may not be experiencing symptoms currently.
Exclusion Criteria:	
 1. Substance abuse or dependence (w/in past 6 months) 2. Those who are pregnant/breastfeeding 3. History of head injury with > 15 minutes of loss of consciousness/mal sequelae 4. DSM-V intellectual disability 5. Having a non-removable ferromagnetic metal within the body (particularly in the head) 6. History of seizures
Statistical Methodology:	Within and between comparisons to statistically detect differences in symptoms, tasks and electrophysiology measures before and after treatment conditions (cathodal tDCS, 10hz and personalized tACS). To determine the effectiveness and feasibility of targeting the rOFC with a novel targeting methodology to engage target outcomes.

Statement: The design, conduct and reporting of this trial shall be conducted in accordance with the protocol, the United States 45 Code of Federal Regulations (CFR) part 46 known as “The Common Rule”, 45 CFR 164.502(d), and 164.514(a)-(c) known as “The Privacy Rule” of the Health Insurance Portability and Accountability Act (HIPAA), and the International Conference on Harmonization (ICH)/Good Clinical Practice (GCP). All Investigators will have documented training in The Collaborative Institutional Training Initiative (CITI Program) in Biomedical Research and GCP.

Background: Mania is a core symptom of bipolar disorder involving periods of euphoria. Decreased inhibitory control, increased risk-taking behaviors, and aberrant reward processing are some of the more recognized symptoms of bipolar disorder and are included in the diagnostic criteria for mania. Current drug therapies for mania are frequently intolerable, ineffective, and carry significant risk for side effects. Presently there are no neurobiologically informed therapies that treat or prevent mania. However, using a newly validated technique termed lesion network mapping, researchers demonstrated that focal brain lesions having a causal role in the development of mania in people without a psychiatric history can occur in different brain locations, such as the right orbitofrontal cortex (OFC), right dorsolateral prefrontal cortex (DLPFC), and right inferior temporal gyrus (ITG). This lesion network evidence converges with existing cross-sectional and longitudinal observations in bipolar mania that have identified specific disruptions in network communication between the amygdala and ventrolateral prefrontal cortex. The OFC is associated with inhibitory control, risk-taking behavior, and reward learning which are major components of bipolar mania. Thus, the association between

OFC with mania symptoms, inhibitory control, risk-taking behavior, and reward processing suggests that this region could be targeted using non-invasive brain stimulation.

Transcranial Electrical Stimulation (tES): tES is a non-invasive brain stimulation technique which modulates cortical excitability by a weak electrical current [< 4 milliamps (mA)] between two electrodes via direct current (DC), alternating current (AC), random noise (RN) or oscillatory current (OC). This study will utilize cathodal tDCS, 10hz and personalized tACS. Five days of twice a day (2x20min) of tES will be used during the week.

Electroencephalography (tES): EEG is a routine, non-invasive procedure to record brain activity. EEG electrodes will be attached to the skin indirectly. Most of the electrodes are mounted in an elastic cap, which is fitted over the head and held in place with elastic straps. Some additional electrodes are placed next to the eyes, on the forehead, or behind the ears, and are held in place with adhesive collars. Electrical contact between the skin and the electrodes is achieved via a water-soluble electrode gel.

Study Rationale: Mania is a core symptom of bipolar disorder involving periods of euphoria, delusions, and overactivity. Mania occurs in multiple medical and psychiatric illnesses and can be refractory to existing treatments. Two recent studies using brain lesion mapping of psychiatrically healthy individuals presenting with mania identified causal locations in the brain, including the orbitofrontal cortex (OFC), dorsolateral prefrontal cortex (DLPFC), and inferior temporal gyrus (ITG), that were associated with new onset mania symptoms. Moreover, these identified brain regions have also been implicated in bipolar mania with specific disruption in network communication between the amygdala and ventro-lateral prefrontal cortex. The OFC is of particular interest because it is a brain structure that is associated with inhibitory control, risk-taking behavior, and reward, which are major behavioral components of mania. Thus, the association between OFC with mania symptoms, inhibitory control, risk-taking behavior and reward suggests that this region could be targeted using noninvasive brain stimulation. While several studies have non-invasively targeted the DLPFC for mania, no study to date has non-invasively stimulated the OFC with either transcranial direct current stimulation (tDCS) or alternating current (tACS) in bipolar disorder and examined its effects on mania, inhibitory control, or risk-taking behavior. However, a study in healthy volunteers showed that cathodal stimulation to the OFC enhanced inhibitory control and decreased risk-taking behavior. Recently, research have showed that targeting the OFC with tACS, personalized to the individual's intrinsic beta-gamma frequency of the reward network, that individuals showed rapid, reversible, frequency-specific modulation of reward-guided choice behavior and learning. Here we aim to answer the question of whether noninvasive brain stimulation when optimally targeted and personalized to an individual's beta-gamma frequency to the OFC can improve emotional cognitive processing and mania symptoms compared to tDCS or sham targeting. The knowledge gained from this study will provide a marker for clinical response and allow personalized treatment for patients with bipolar disorder.

Study Protocol:

Study Timeline

Study Visit Timeline	Visit 1	Visit 2	Visit 3	Visit 4	Visit 5	Visit 6 (1-month follow up)	Visit 7 (3-month follow up)
Consent	X						
Clinical Evaluation	X				X	X	X
Tasks/Cognition Testing	X				X	X	X
EEG	X				X	X	X
tES	X	X	X	X	X		
Sensation Questionnaire	X	X	X	X	X		
Self-Reports	X				X	X	X

Study Visits and Details:

Participants will complete baseline clinical, neuropsychological, behavioral tasks and neurophysiological assessments (day 0), short-term follow-up (day 5) and long-term follow-up (1 & 3 month).

Pre-Screening

Subjects will be prescreened. If the subject appears to qualify for the study, they will be invited in for a screening and a baseline visit.

Screening and Baseline Procedures (approximately 3-4 hours)

Screening and baseline procedures will be conducted in the Massachusetts Mental Health Center (MMHC)/ Beth Israel Deaconess Medical Center (BIDMC) in Boston, MA. The urine toxicology screen and pregnancy test will be completed at MMHC or within BIDMC.

- Eligibility pre-screen will include a telephone pre-screening questionnaire that will assess basic inclusion and exclusion criteria.

- Eligibility screening will include a screening questionnaire that will assess more details related to inclusion and exclusion criteria and will be conducted in-person during the clinical diagnostic session (i.e., the first visit to the laboratory).

- Informed consent will be obtained

- Urine toxicology screen

- Urine pregnancy testing for females of childbearing age

Subjects will be informed that if they do not pass the urine toxicology screen (other than prescribed medication), they will be withdrawn from the study and will not receive compensation for the initial visit. This will be made clear in the pre-screening questionnaire.

- tES screening questions for tES participation

- Demographics: Subjects will be asked to provide standard demographic information (age, sex, race/ethnicity, level of education, cohabitation status) using forms employed in previous studies.

- Psychiatric, medical, substance use history and medication review

- Signing a release to allow for access to recent psychiatric records, if confirmation of medications or psychiatric history is necessary

OBJECTIVES

Primary Objective

The primary objective of this study is to evaluate the effectiveness of tES for improving the mania symptoms (YMRS, ASRM and hospitalizations).

Secondary Objectives

The secondary objective of the study is to evaluate the safety and tolerability of tES targeting the rOFC as well as secondary clinical outcomes including depression, mania, cognition, impulsiveness, electrophysiology outcomes, social functioning and global functioning

Clinical and Cognitive Outcomes: Symptom ratings will be collected using the PANSS, ASRM, YMRS, MADRS, SFS, GAF, BIS and cognition with the BAC

Electrophysiology Outcomes: A reinforcement learning task will be implemented probing the reward feedback mechanisms related to the rOFC. A resting state task will be implemented to measure brain dynamics at rest.

Computerized behavioral tasks: The BART and Go/No Go task will be used to determine the effective targeting of the rOFC and impulsiveness behaviors.

Diagnostic Assessments

Structured Clinical Interview for DSM-IV (SCID)

This is a structured clinical diagnostic screening interview for subjects 15 and older. It is used to diagnose Axis I disorders including modules on depression, mania, psychosis, alcohol and substance use, anxiety, somatic and eating disorders.

Clinical Assessments

Positive and Negative Symptom Scale (PANSS)

The ratings are based on a clinical interview conducted by trained clinical staff, covering all of the items on the rating scale.

- This rating scale is meant to capture many different types of symptoms including positive, negative, and general psychopathology symptoms. The ratings are based on a clinical interview with the participants.
- Ratings should be based on the patient's condition in the past week.
- Always use the manual with anchor points when scoring and do not try to score from your memory of the anchor points or by their headings (mild, moderate or severe).

Altman Self-Rated Mania Scale (ASRM):

The Altman Self-Rating Mania Scale (ASRM) is a brief, self-report questionnaire used to assess the presence and severity of manic symptoms. It is a five-item scale where individuals rate their experiences over the past week, with higher scores indicating greater symptom severity. Self-administered in survey form.

Barret Impulsiveness Scale (BIS):

A brief, self-report questionnaire used to assess the presence and severity of manic symptoms. The scale contains 30 items that measure three main domains: attention impulsivity, motor impulsivity, and non-planning impulsivity.

Montgomery and Asberg Depression Rating Scale (MADRS)**Interviewer:**

The questions in bold for each item **should be asked exactly as written**. Often these questions will elicit enough information about the severity and frequency of a symptom for you to rate the item with confidence. Follow-up questions are provided; however, for use when further exploration or additional clarification of symptoms is necessary. The specified questions should be asked until you have enough information to rate the item confidently. In some cases, you may also have to add your own follow-up questions to obtain the necessary information.

**Ratings should be based on the patient's condition in the past week.*

Referent of "usual" or "normal" conditions. Several of the interview questions refer to the patient's usual or normal functioning. In some cases, such as when the patient has Dysthymia or Seasonal Affective Disorder, the referent should be to the last time they felt OK (i.e., not depressed or high) for at least a few weeks.

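### As listed, the three randomised conditions share one rOFC target and mix individual tuning with frequency band or waveform, so no contrast among them can credit the lesion-network target or tuning alone

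*Combined protocol and SAP*

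**What the plan says.** The Synopsis (Design) states that tES "was delivered to the right orbital frontal cortex (rOFC) from baseline to day 5" and that "Participants were randomly assigned to either cathodal transcranial direct current (tDCS), 10hz or personalized transcranial alternating current (tACS) conditions". It gives one target and no alternative site. The tES paragraph of the Background lists the same set: "This study will utilize cathodal tDCS, 10hz and personalized tACS".

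The purpose attached to that randomisation is "to test the effectiveness and feasibility of stimulating the rOFC using a novel targeting methodology consisting of a lesion network guided brain target". Statistical Methodology in the Synopsis repeats it: "To determine the effectiveness and feasibility of targeting the rOFC with a novel targeting methodology to engage target outcomes". Under Secondary Objectives (Computerized behavioral tasks), the BART and Go/No Go tasks "will be used to determine the effective targeting of the rOFC and impulsiveness behaviors".

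The Study Rationale asks whether stimulation "optimally targeted and personalized to an individual's beta-gamma frequency to the OFC can improve emotional cognitive processing and mania symptoms". Its comparator is either tDCS or a sham targeting condition that is not defined anywhere. It adds that the knowledge gained "will provide a marker for clinical response and allow personalized treatment for patients with bipolar disorder".

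Two later sections describe a different set of groups. General Statistical Considerations summarises continuous data for treatment and for sham. Primary Analyses compares two treatment groups. The formal Primary Objective is narrower than the Synopsis wording: it concerns the effectiveness of tES on mania symptoms and names neither targeting nor personalization.

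**The concern.** An effect can be credited to a feature of the treatment only if some comparison varies that feature. On the listed arms, what varies is the type of current. The brain target stays the same, and individual tuning never changes without something else changing too.

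At stake is the interpretation. A difference between arms, or improvement in all of them, could be reported as showing that lesion-network targeting is effective. A change on BART or Go/No Go could be reported as showing that the rOFC was effectively targeted, although practice, time and non-specific effects of current could produce the same change. A better result in the personalized arm could be read as supporting individual tuning when the frequency band alone might explain it.

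**Working it through.** No figure in the plan needs reproducing. The question is which effects the listed arms can estimate.

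**Inputs.** The three conditions and the single target come from the Synopsis (Design) and the Background. The beta-gamma tuning of the personalized arm comes from the Study Rationale. One assumption is needed: 10 Hz lies outside beta-gamma. The documents give no band limits.

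**Coding** (1 = feature present):

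| Condition | Current on | rOFC target | Alternating | Beta-gamma band | Individually tuned |
|---|---|---|---|---|---|
| Cathodal tDCS | 1 | 1 | 0 | 0 | 0 |
| 10 Hz tACS | 1 | 1 | 1 | 0 | 0 |
| Personalized tACS | 1 | 1 | 1 | 1 | 1 |

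**Pairwise contrasts** (row minus row, same column order):

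- Personalized minus 10 Hz = (0, 0, 0, 1, 1): band and tuning together.
- Personalized minus tDCS = (0, 0, 1, 1, 1): waveform, band and tuning together.
- 10 Hz minus tDCS = (0, 0, 1, 0, 0): alternating current at 10 Hz against direct current.

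The target entry is 0 in all three. No contrast has a 1 for tuning and 0 elsewhere. With an intercept the design matrix has rank 3. The target effect, the current on/off effect, band alone and tuning alone are not estimable. The sum of band and tuning is estimable, and so is waveform at 10 Hz.

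**Would another arm change this?** The rows below are a diagnosis, not proposals.

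- No-current sham, (0, 0, 0, 0, 0): rank 4. tDCS minus sham = (1, 1, 0, 0, 0), which is stimulation at the rOFC against none. Target alone and tuning alone remain not estimable.
- Off-target active tDCS, (1, 0, 0, 0, 0): rank 4. tDCS minus this arm = (0, 1, 0, 0, 0), so the target becomes estimable against that other site. Tuning alone does not.
- Fixed-frequency beta-gamma tACS at the rOFC, (1, 1, 1, 1, 0): rank 4. Personalized minus this arm = (0, 0, 0, 0, 1), so tuning becomes estimable. The target does not.

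**Sensitivity to the band assumption.** If the protocol's beta-gamma range included 10 Hz, the 10 Hz row would become (1, 1, 1, 1, 0). Personalized minus 10 Hz would then be (0, 0, 0, 0, 1), and the tuning half of the point would fall for that contrast. The target half does not depend on the assumption.

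**The case against.** The strongest reply is that the arm set is not closed. The Study Rationale mentions sham targeting, General Statistical Considerations assumes a sham group, and Primary Analyses speaks of two treatment groups. If sham targeting means active stimulation at another site, the target half of the point fails. This stands as a limit: the finding applies to the conditions listed in the Synopsis and Background. If the sham is merely current off, it does not help.

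Second, a reader might infer that no randomised contrast tests personalization at all. The documents do not support that. The Study Rationale asks a package question, and personalized against tDCS answers it as a package. Personalized against 10 Hz is also a randomised comparison, at the same target and with alternating current in both arms. What cannot be done is isolate tuning.

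Third, a reader might infer that the trial fails its own main question. That also goes too far. The Primary Objective is the effectiveness of tES on mania symptoms, the secondary objectives make no site-against-site claim, and feasibility needs no between-arm contrast. The Design sentence could be read as merely explaining how the site was chosen. But the Synopsis twice pairs feasibility with effectiveness when it names the targeting method, so the stronger conclusion is open to anyone who follows the text.

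Fourth, Statistical Methodology also plans within-group comparisons. These show change over time in people stimulated at one site, and they cannot assign that change to the site.

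Finally, the reinforcement learning task is described as probing reward feedback related to the rOFC, not as establishing effective targeting, so it is outside this point. The phrase about personalized treatment is an aspiration in the rationale, not an endpoint or decision rule.

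**Conclusion.** The concern holds in a limited form. Among the three listed conditions, 0 of 3 pairwise contrasts vary the target and 0 of 3 vary individual tuning alone. The plan therefore cannot support effectiveness of the lesion-network targeting method as a conclusion, cannot use BART and Go/No Go to establish effective targeting, and cannot credit tuning by itself. It can support feasibility and comparisons of stimulation packages at the rOFC.

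This rests on three readings: the single target in the Design sentence applies to every arm; 10 Hz is outside beta-gamma (needed only for the personalized against 10 Hz contrast); and no off-target arm exists. The documents leave the last open, because sham targeting is undefined and the group descriptions conflict. The consequence is for interpretation. The validity of the randomised comparisons themselves is not in question here.

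**What to change.** 1. First reconcile the three conditions in the Synopsis and Background with the sham targeting comparator in the Study Rationale, the sham group in General Statistical Considerations and the two treatment groups in Primary Analyses. Define sham targeting, or remove it if no such condition exists.
2. Unless an off-target arm exists, state in the Synopsis (Design and Statistical Methodology) that the randomised comparison is of stimulation types at one rOFC target. Keep feasibility. Drop effectiveness of the targeting method as a conclusion.
3. Under Computerized behavioral tasks, treat BART and Go/No Go as behavioural outcomes, not as a determination of effective targeting.
4. Name the personalized contrast as individual beta-gamma tACS against 10 Hz tACS (or against tDCS), give the band limits, and make no claim that tuning alone caused a difference.
5. In the Study Rationale, mark the statement about allowing personalized treatment as hypothesis-generating.

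Cost: wording only, with no new arm, visit or procedure. The trial gives up a headline claim. The Synopsis is written in the past tense, so the change may come after treatment. It should be dated as such, and because it only narrows what may be concluded, late adoption does not favour any result.

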****Rate the highest level of psychopathology. When in doubt, rate up and record the higher score.***

Global Assessment Functioning (GAF)

Consider psychological, social, and occupational functioning on a hypothetical continuum of mental health-illness. Do not include impairment in functioning due to physical (or environmental) limitations.

Indicate appropriate code for the **LOWEST level of functioning during the week of POOREST functioning in the past month.** (Use intermediate level when appropriate, i.e., 45, 68, 72).

Young Mania Rating Scale (YMRS)**General Instructions to the Clinician:**

The purpose of each item is to rate the severity of that abnormality in the patient. When several keys are given for a particular grade of severity, the presence of only one is required to qualify for that rating.

The keys provided are guides. One can ignore the keys if that is necessary to indicate severity, although this should be an exception rather than a rule.

Scoring between the points given (whole or half points) is possible and encouraged after experience with the scale is acquired; this is particularly useful when severity of a particular item in a patient does not follow the progression indicated by the keys.

Social Function Scale (SFS):

Used to measure the degree of functioning across several domains. Social engagement/withdrawal (amount of time to spend alone, the likelihood to initiate conversation) Interpersonal behavior (number of friends, engagement in a romantic relationship) Prosocial activities (participation in social activities e.g. visit friends, play sports). Additionally, it provides competency scores for items.

Brief Assessment of Cognition in Schizophrenia (BACS)

Instructions (Atkins et al. 2017):

Verbal Memory (Verbal Memory & Learning Domain): 7 min

Subjects hear a list of 15 words to remember. Words are presented by the App at a standard rate.

- Outcome measure: Total number of words recalled across 5 learning trials.

Digit Sequencing (Working Memory Domain): 5 min

Subjects are presented with randomly ordered auditory clusters of numbers (i.e., 936) with steadily increasing trial length. Items are presented by the App at a standard rate. Subjects are asked to report the numbers in order, from lowest to highest.

- Outcome measure: Number of trials with all items in the correct order.

Token Motor Task (Motor Function): 3 min

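### The eligibility text both requires current mania symptoms and admits people without them, so the population for the mania outcomes is undefined

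*Combined protocol and SAP*

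**What the plan says.** The synopsis (Inclusion Criteria) lists eight criteria. Criterion 5 requires a history of more than one lifetime manic episode. Criterion 6 reads "Experiencing mild to moderate symptoms of mania". Below the list, a sentence about participants in the stimulation procedure, worded as an addition to the criteria, includes those with a history of mania who "may or may not be experiencing symptoms currently".

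Other places that bear on the question:

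- **Patient Population (synopsis).** Accepts a diagnosis of bipolar or schizoaffective disorder, or a history of mania. Current symptoms are not mentioned.
- **Screening and Baseline Procedures.** Eligibility is checked with a telephone pre-screen and then "a screening questionnaire that will assess more details related to inclusion and exclusion criteria". No rating-scale threshold is named.
- **Clinical Assessments.** The ASRM is described "with higher scores indicating greater symptom severity". For the YMRS, "The purpose of each item is to rate the severity of that abnormality in the patient". Neither description gives an entry score or a severity band.
- **Primary Objective.** To "evaluate the effectiveness of tES for improving the mania symptoms", with YMRS, ASRM and hospitalizations named.
- **Primary Endpoint and Primary Analyses.** The endpoint is change from baseline to day 5, 1 month and 3 months. The analysis is MMRM or non-parametric methods, with no model terms listed.
- **Design and Enrollment (synopsis).** 14 individuals. Randomisation is described in the past tense, while most later sections use the future tense.

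**The concern.** The two eligibility statements cannot both operate for a person with past mania who is currently well. Without knowing which one was used, a reader cannot say whether the result describes people being treated for present mania or a wider group with a history of it.

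This matters most for the two symptom scales. Someone who starts at or near the bottom of the YMRS or ASRM can hardly improve on it. If such people were enrolled, a small mean change could reflect the stimulation or the case mix, and with 14 participants a few individuals would be enough to blur the two. The argument does not carry over to hospitalizations. Nor does it rule out a difference in worsening over the 3 months of follow-up, which people without symptoms could still show.

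**Working it through.** **1. Do the statements conflict?** Two readings are available.

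- *All eight criteria still bind.* The wording that presents the sentence as an addition supports this. But then the phrase making symptoms optional has no effect, and its history clause only repeats criterion 5.
- *The sentence widens entry.* The phrase then has meaning, but criterion 6 is cancelled without the text saying so.

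Neither reading makes the text coherent. The screening questionnaire refers back to the same criteria, so it does not settle the matter. The Patient Population row is compatible with the wider reading but does not withdraw criterion 6.

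**2. How large could dilution be?** Let k of the 14 lack symptoms, so f = k/14. With effect E in symptomatic people and E0 in the others, and an even spread over arms, the mean effect is (1 − f)E + fE0. Assuming E0 = 0, the retained fraction is (14 − k)/14:

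| k (assumed) | Retained fraction |
|---|---|
| 2 | 12/14 = 0.86 |
| 4 | 10/14 = 0.71 |
| 7 | 7/14 = 0.50 |

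The documents give no k. With k = 0 there is no dilution, and if E0 is not zero the loss is smaller.

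**3. What would adjusting for baseline gain or cost?** The measure is the variance of the baseline-adjusted arm contrast divided by that of the change-score contrast; below 1 favours adjustment. No input comes from the documents, which give no allocation ratio, so arm sizes are assumptions.

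*Everyone symptomatic (homogeneous baselines).* Ratio = (1 + ρ)/2 × [1 + 1/(v − 2)], where ρ is the baseline–follow-up correlation and v = N − number of arms.

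| Layout | v | ρ = 0.5 | ρ = 0.7 | ρ = 0.9 |
|---|---|---|---|---|
| 7 v 7, all 14 | 12 | 0.75 × 1.100 = 0.83 | 0.85 × 1.100 = 0.94 | 0.95 × 1.100 = 1.05 |
| 5/5/4, one model | 11 | 0.75 × 1.111 = 0.83 | 0.85 × 1.111 = 0.94 | 0.95 × 1.111 = 1.06 |
| 5 v 5 only | 8 | 0.75 × 1.167 = 0.88 | 0.85 × 1.167 = 0.99 | 0.95 × 1.167 = 1.11 |
| 5 v 4 only | 7 | 0.75 × 1.200 = 0.90 | 0.85 × 1.200 = 1.02 | 0.95 × 1.200 = 1.14 |

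*Mixed symptom status (simulation, 20,000 trials per setting).* Each person lacks symptoms with probability f = 25% or 50% (baseline and change both 0). Otherwise the baseline mean is 2 or 3 SD with SD 1, change has SD 1, and the slope of change on baseline is −0.5. Improvement is m in the reference arm and m + d in the other.

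| Setting | 7 v 7 or one 5/5/4 model |
|---|---|
| m = 1, d = 0.5–1, f = 25% | 0.59–0.64 |
| m = 1, d = 0.5–1, f = 50% | 0.44–0.48 |
| m = 1, d = 0 | 0.53–0.71 |
| m = 0, d = 0.5–1 | 0.82–0.99 |
| m = 0, d = 0 | 0.97–1.06 |

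Pairwise comparisons with m = 0 and d = 0 do worse: about 1.03–1.17 for 5 v 5 and up to about 1.3 for 5 v 4, because one slope is estimated from very few people. The largest gains also depend on giving people without symptoms no variation at all. With an SD of 0.5 in them, the ratio at f = 50% (7 v 7, m = 1, d = 0.5) rises from about 0.46–0.47 to as much as 0.60.

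**The case against.** The sentence concerns the stimulation procedure specifically and follows the general list, so it can be taken as a deliberate widening. The Patient Population row points the same way, and the trial also tests feasibility, for which a broad population is reasonable. This is fair as far as it goes: the broad rule may be the intended one. It does not remove the contradiction, because the sentence is worded as adding to criterion 6 rather than replacing it.

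A reader might infer that people without symptoms were enrolled and that the mania results are therefore diluted. The documents do not support that. They give neither the number of such people nor any baseline scores, and the past-tense Design row does not say which rule was applied.

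A reader might also infer that the analysis omits baseline severity. That does not follow either. The analysis section names MMRM without listing terms, so a baseline covariate may or may not already be intended. Baseline adjustment is also not a direct consequence of the eligibility conflict, and with very small pairwise comparisons it can lose precision. Both points stand. They are the reason for presenting adjustment as a statement to be made, in a single model, and not as the correction of a demonstrated error.

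**Conclusion.** The concern holds: the synopsis contains two incompatible entry rules and nothing else in the document decides between them. That conclusion rests on the text alone and is firm. This review does not say which rule is right.

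The consequence for the YMRS and ASRM is conditional and cannot be sized. The retained fractions of 0.86, 0.71 and 0.50 assume 2, 4 or 7 people without symptoms, no effect in them and an even spread over arms; the true loss may be zero.

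Under the assumed inputs, baseline adjustment gives a variance ratio of about 0.45–0.7 if symptom status is mixed and symptomatic people improve in both arms. Otherwise it is about 0.8–1.06 in a model using all arms, and it reaches about 1.3 if arms of 4 or 5 are compared pairwise. The gain is large only in the first situation.

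**What to change.** 1. **Reconcile criterion 6 with the sentence below the list**, and in doing so state how symptom status is established (scale, score range and visit). State which rule was applied at enrolment. Report baseline YMRS and ASRM by arm, with the number at the scale minimum. Cost: wording and one table, from clinical and self-report assessments already scheduled at Visit 1.
2. **State that the YMRS and ASRM analyses adjust for the baseline score of the same scale**, in one model using all arms, with a rank-based equivalent (for example rank ANCOVA) if the analysis is non-parametric. Cost: one degree of freedom, and in an all-arm model at worst a small loss of precision (ratio about 1.06 under the inputs above). Separate pairwise models are best avoided.
3. **Keep all randomised participants in the primary mania analysis.** Any subset symptomatic at baseline should be descriptive only: at f = 50% it would hold about 7 people, or 2–3 per arm with three arms (7/3 ≈ 2.3).

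A separate matter needs its own reconciliation. The Primary Endpoint paragraph lists PANSS and ASRM as the clinical measures, whereas the synopsis and the Primary Objective list YMRS and ASRM.
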